There were no meaningful changes in mean LFT values in controlled studies in adult or pediatric subjects; LFT abnormalities were similar in drug- and placebo-treated subjects in controlled studies (1.4%). No pediatric subjects were discontinued from controlled studies due to LFT abnormalities.²⁴

Impaired Renal Function

Levetiracetam is known to be substantially excreted by the kidney, and the risk of adverse reactions to this drug may be greater in patients with impaired renal function.²⁴

Post-Marketing Experience With Adjunctive Therapy

The following have been reported in patients receiving marketed levetiracetam worldwide (alphabetical order): abnormal LFT values, choreoathetosis, dyskinesia, erythema multiforme, hepatic failure, hepatitis, leukopenia, neutropenia, pancreatitis, pancytopenia (with bone marrow suppression identified in some of these cases), Stevens-Johnson syndrome, thrombocytopenia, toxic epidermal necrolysis, and weight loss. Alopecia has been reported with levetiracetam use; recovery was observed in the majority of cases where levetiracetam was discontinued.

Levetiracetam Monotherapy

Levetiracetam is not approved as monotherapy for epilepsy; however, investigator-initiated studies of children with epilepsy support its use in this indication. These monotherapy studies used the same titration and maintenance dosing as pivotal adjunctive studies; overall efficacy and safety outcomes were similar in both treatment settings.^{21,24,29,43}

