Adverse events of clinical interest for topiramate are: effects on liver function; metabolic acidosis; effects on growth and maturation; vision abnormalities; oligohidrosis with hyperthermia and rash; hyperammonemia and encephalopathy; kidney stones; cognitive disorders; and suicidality.

Adverse events of clinical interest for levetiracetam are as listed previously, notably somnolence, asthenia, and behavior disturbances (especially hostility and nervousness).

Subjects with adverse events of special interest may be counted or listed.

Clinical Laboratory Tests

Laboratory data will be summarized by type of laboratory test. Reference ranges and markedly abnormal results (specified in the Statistical Analysis Plan) will be used in the summary of laboratory data. Descriptive statistics will be calculated for each laboratory analyte at baseline and at each scheduled time point. Changes from baseline results will be presented in pre- versus

posttreatment cross-tabulations (with classes for below, within, and above normal ranges). A listing of subjects with any laboratory results outside the reference ranges will be provided. A listing of subjects with any markedly abnormal laboratory results will also be provided.

Vital Signs

Descriptive statistics of temperature, heart rate, respiratory rate, and blood pressure (systolic and diastolic) values and changes from baseline will be summarized at each scheduled time point. The percentage of subjects with values beyond clinically important limits (using age-appropriate ranges) will be summarized.

Physical Examination/Neurologic Examination

Descriptive statistics of changes from baseline will be summarized at each scheduled time point.

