7.9. Adverse Events

Adverse events are coded to System Organ Class (SOC) and preferred terms (PT) using the Medical Dictionary for Regulatory Activities (MedDRA) coding system, version 21.1 or higher. Treatment-emergent adverse events (TEAEs) are those AEs which start or worsen after receipt of the first study drug and before the end of the REACH. REACH is defined as follows: AEs with onset date within therapeutic reach (i.e. 3 days) or SAEs/deaths with onset date within 30 days, inclusive, after end of treatment. AE's with partial onset date will be handled as follows: a missing day should be set to first of month. If month is missing the missing month should be set to January.

Summaries of TEAEs will be provided as incidence tables (number of subjects experiencing an event) by treatment group within each age group and overall (age 2-15). For each TEAE, the percentage of subjects who experience at least 1 occurrence of the given event will be summarized. Tables will be sorted by decreasing frequency in incidence (the highest to lowest incidence) first within the SOC and then the PT. Treatment-emergent serious AEs (SAEs), TEAEs leading to discontinuation, TEAEs by severity, TEAEs by relationship and TEAEs of special interest will be summarized. Adverse events of special interest for topiramate include: effects on liver function; metabolic acidosis; effects on growth and maturation; vision abnormalities; oligohidrosis, hyperthermia and secondary rash; hyperammonemia and/or encephalopathy; kidney stones; neuropsychiatric and cognitive disorders; and suicidality. Adverse events of clinical interest for levetiracetam are as listed previously, notably somnolence, asthenia, and behavior disturbances

(especially hostility and nervousness). Please see [Appendix 3](#) for the MedDRA codes for these AE of clinical interest.

A listing of AEs will also be provided.

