Appendix 3: AE of clinical interest

AETERM	AEBODSYS in MedDRA 22.0	AEDECOD (PT) In MedDRA 22.1
5' nucleotidase increased	Investigations	5' nucleotidase increased
Abulia	Psychiatric disorders	Abulia
Accommodation disorder	Eye disorders	Accommodation disorder
Acidosis	Metabolism and nutrition disorders	Acidosis
Acidosis hyperchloraemic	Metabolism and nutrition disorders	Acidosis hyperchloraemic
Acquired epidermolysis bullosa	Skin and subcutaneous tissue disorders	Acquired epidermolysis bullosa
Acquired pigmented retinopathy	Injury, poisoning and procedural complications	Acquired pigmented retinopathy
Activation syndrome	Psychiatric disorders	Activation syndrome
Acute generalised exanthematous pustulosis	Skin and subcutaneous tissue disorders	Acute generalised exanthematous pustulosis
Acute hepatic failure	Hepatobiliary disorders	Acute hepatic failure
Renal failure acute	Renal and urinary disorders	Acute kidney injury
Adjustment disorder with anxiety	Psychiatric disorders	Adjustment disorder with anxiety
Adjustment disorder with depressed mood	Psychiatric disorders	Adjustment disorder with depressed mood
Adjustment disorder with mixed anxiety and depressed mood	Psychiatric disorders	Adjustment disorder with mixed anxiety and depressed mood
Adjustment disorder with mixed anxiety and depressed mood	Psychiatric disorders	Adjustment disorder with mixed anxiety and depressed mood
Affect lability	Psychiatric disorders	Affect lability
Agitated depression	Psychiatric disorders	Agitated depression
Agitation	Psychiatric disorders	Agitation
Alanine aminotransferase abnormal	Investigations	Alanine aminotransferase abnormal
Alanine aminotransferase increased	Investigations	Alanine aminotransferase increased
Albumin urine present	Investigations	Albumin urine present
Alpha 1 foetoprotein abnormal	Investigations	Alpha 1 foetoprotein abnormal
Alpha 1 foetoprotein increased	Investigations	Alpha 1 foetoprotein increased

Alpha 1 globulin increased	Investigations	Alpha 1 globulin increased
Alpha 2 globulin increased	Investigations	Alpha 2 globulin increased
Alpha globulin increased	Investigations	Alpha globulin increased
Alpha-2 macroglobulin increased	Investigations	Alpha-2 macroglobulin increased
Altered state of consciousness	Nervous system disorders	Altered state of consciousness
Altered visual depth perception	Eye disorders	Altered visual depth perception
Amaurosis	Eye disorders	Amaurosis
Amaurosis fugax	Eye disorders	Amaurosis fugax

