Bone disorder	Musculoskeletal and connective tissue disorders	Bone disorder
Bone disorder	Musculoskeletal and connective tissue disorders	Bone disorder

Bone formation decreased	Musculoskeletal and connective tissue disorders	Bone formation decreased
Bone metabolism disorder	Musculoskeletal and connective tissue disorders	Bone metabolism disorder
Bone pain	Musculoskeletal and connective tissue disorders	Bone pain
Borderline glaucoma	Eye disorders	Borderline glaucoma
Borderline mental impairment	Nervous system disorders	Borderline mental impairment
Bradyphrenia	Psychiatric disorders	Bradyphrenia
Bromosulphthalein test abnormal	Investigations	Bromosulphthalein test abnormal
Budd-Chiari syndrome	Hepatobiliary disorders	Budd-Chiari syndrome
Cachexia	Metabolism and nutrition disorders	Cachexia
Calculus bladder	Renal and urinary disorders	Calculus bladder
Calculus bladder	Renal and urinary disorders	Calculus bladder
Calculus prostatic	Reproductive system and breast disorders	Calculus prostatic
Calculus prostatic	Reproductive system and breast disorders	Calculus prostatic
Calculus ureteric	Renal and urinary disorders	Ureterolithiasis
Calculus urethral	Renal and urinary disorders	Calculus urethral
Calculus urinary	Renal and urinary disorders	Calculus urinary
Carbon dioxide decreased	Investigations	Carbon dioxide decreased
Cardiac arrest	Cardiac disorders	Cardiac arrest
Cardiac death	General disorders and administration site conditions	Cardiac death
Cardiac failure	Cardiac disorders	Cardiac failure
Cardiac failure acute	Cardiac disorders	Cardiac failure acute
Cardiac failure chronic	Cardiac disorders	Cardiac failure chronic
Cardiac failure congestive	Cardiac disorders	Cardiac failure congestive
Cardiac output decreased	Investigations	Cardiac output decreased
Cardiac ventriculogram abnormal	Investigations	Cardiac ventriculogram abnormal

Cardiac ventriculogram left abnormal	Investigations	Cardiac ventriculogram left abnormal
Cells in urine	Investigations	Cells in urine
Change in sustained attention	Psychiatric disorders	Change in sustained attention
Charles Bonnet syndrome	Eye disorders	Charles Bonnet syndrome
Childhood disintegrative disorder	Psychiatric disorders	Child-Pugh-Turcotte score increased
Child-Pugh-Turcotte score increased	Investigations	
Chills	General disorders and administration site conditions	Chills
Chloropsia	Eye disorders	Chloropsia
Cholaemia	Hepatobiliary disorders	Cholaemia
Cholelithiasis	Hepatobiliary disorders	Cholelithiasis

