Hepatic encephalopathy prophylaxis	Surgical and medical procedures	Hepatic encephalopathy prophylaxis
Hepatic enzyme abnormal	Investigations	Hepatic enzyme abnormal
Hepatic enzyme decreased	Investigations	Hepatic enzyme decreased
Hepatic enzyme increased	Investigations	Hepatic enzyme increased
Hepatic failure	Hepatobiliary disorders	Hepatic failure
Hepatic fibrosis	Hepatobiliary disorders	Hepatic fibrosis
Hepatic function abnormal	Hepatobiliary disorders	Hepatic function abnormal

Hepatic haemorrhage	Hepatobiliary disorders	Hepatic haemorrhage
Hepatic hydrothorax	Respiratory, thoracic and mediastinal disorders	Hepatic hydrothorax
Hepatic infarction	Hepatobiliary disorders	Hepatic infarction
Hepatic infiltration eosinophilic	Hepatobiliary disorders	Hepatic infiltration eosinophilic
Hepatic lesion	Hepatobiliary disorders	Hepatic lesion
Hepatic mass	Hepatobiliary disorders	Hepatic mass
Hepatic necrosis	Hepatobiliary disorders	Hepatic necrosis
Hepatic pain	Hepatobiliary disorders	Hepatic pain
Hepatic steatosis	Hepatobiliary disorders	Hepatic steatosis
Cytolytic hepatitis	Hepatobiliary disorders	Hepatitis
Hepatitis	Hepatobiliary disorders	Hepatitis
Hepatitis acute	Hepatobiliary disorders	Hepatitis B
Hepatitis fulminant	Hepatobiliary disorders	Hepatitis chronic active
Hepatitis toxic	Hepatobiliary disorders	Hepatitis toxic
Hepatobiliary disease	Hepatobiliary disorders	Hepatobiliary disease
Hepatobiliary scan abnormal	Investigations	Hepatobiliary scan abnormal
Hepatocellular foamy cell syndrome	Hepatobiliary disorders	Hepatocellular foamy cell syndrome
Hepatocellular injury	Hepatobiliary disorders	Hepatocellular injury
Hepatomegaly	Hepatobiliary disorders	Hepatomegaly
Hepatopulmonary syndrome	Respiratory, thoracic and mediastinal disorders	Hepatopulmonary syndrome
Hepatorenal failure	Hepatobiliary disorders	Hepatorenal failure
Hepatorenal syndrome	Hepatobiliary disorders	Hepatorenal syndrome

Hepatosplenomegaly	Hepatobiliary disorders	Hepatosplenomegaly
Hepatotoxicity	Hepatobiliary disorders	Hepatotoxicity
Hidradenitis	Skin and subcutaneous tissue disorders	Hidradenitis
Hippus	Eye disorders	Hippus
Holmes-Adie pupil	Eye disorders	Holmes-Adie pupil
Homocysteine urine	Investigations	Homocysteine urine
Homocysteine urine present	Investigations	Homocysteine urine present
Hot flush	Vascular disorders	Hot flush
Hydrocholecystis	Hepatobiliary disorders	Hydrocholecystis
Hydronephrosis	Renal and urinary disorders	Hydronephrosis

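### Two adjacent liver rows in SAP Appendix 3 carry the preferred term of a different disease, so acute and fulminant hepatitis may be left out of the special-interest summary

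*SAP*

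**What the plan says.** SAP 7.9 codes adverse events to system organ class and PT, sorts its incidence tables by those levels, and plans a summary of special-interest events: "TEAEs by relationship and TEAEs of special interest will be summarized". It refers to Appendix 3 for the terms that define those events. Liver effects come first among the topiramate categories, both there and in Protocol 11.4: "Adverse events of clinical interest for topiramate are: effects on liver function; metabolic acidosis".

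Appendix 3 has three columns: a source term (AETERM), the system organ class, and a third headed "AEDECOD (PT) In MedDRA 22.1". In the row for "Hepatitis acute" the third column reads Hepatitis B. In the next row, for "Hepatitis fulminant", it reads "Hepatitis chronic active". Both rows are placed in the hepatobiliary class.

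**The concern.** Differences between the first and third columns are common in Appendix 3, and most are renamings or roll-ups. Acute renal failure becomes acute kidney injury, for example, and gallbladder pain becomes biliary colic. These two rows do not fit that pattern. Acute hepatitis can have many causes and is not hepatitis B, and a fulminant course is not chronic active disease.

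A program that selects events by the printed PTs would look for the wrong diseases in these two rows. The special-interest summary could then omit two serious presentations of liver harm, in the category named first for topiramate, and could take in a viral infection in place of one of them.

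**Working it through.** The plan gives no figure to reproduce, so the check sets the rows side by side.

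**Step 1: every Appendix 3 row with hepatitis in the source-term or PT column (9 rows).**

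| Source term | Class | Printed PT | Agreement |
|---|---|---|---|
| Autoimmune hepatitis | Hepatobiliary | Autoimmune hepatitis | same |
| Chronic hepatitis | Hepatobiliary | Chronic hepatitis | same |
| Cytolytic hepatitis | Hepatobiliary | Hepatitis | plausible roll-up |
| Hepatitis | Hepatobiliary | Hepatitis | same |
| Hepatitis acute | Hepatobiliary | Hepatitis B | **different disease** |
| Hepatitis fulminant | Hepatobiliary | Hepatitis chronic active | **different disease** |
| Hepatitis toxic | Hepatobiliary | Hepatitis toxic | same |
| Ischaemic hepatitis | Hepatobiliary | Ischaemic hepatitis | same |
| Perihepatitis gonococcal | Infections | Perihepatitis gonococcal | same |

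Three of the 9 rows differ. One is a reasonable roll-up and two are not. Hepatitis B also sits in the hepatobiliary class, although the list files the gonococcal infection under infections.

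**Step 2: could this be a table-reading fault?** It is unlikely. The rows directly above (Hepatitis) and below (Hepatitis toxic) align, and no cell in this run is blank. Hepatitis B and chronic active hepatitis do not occur in the first column at all, so a shifted cell could not have supplied them.

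**Step 3: which terms are selected under each possible key?**

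| Event coded as | Match on first column | Match on PT column |
|---|---|---|
| Hepatitis acute | selected | not selected |
| Hepatitis fulminant | selected | not selected |
| Hepatitis B | not selected | selected |
| Hepatitis chronic active | not selected | selected |

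The choice of column reverses all four results.

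**Step 4: which key does the plan imply?** SAP 7.9 does not name the column. Two points favour PT. First, events are coded and tabulated at PT level. Second, Protocol 11.4 says that what investigators report is verbatim text, which is then coded, so matching reported text to a fixed list of terms would be unreliable. PT is therefore the natural key, but that is an inference.

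**Step 5: where would a missed case still appear?** The PT column still holds Hepatitis, Hepatitis toxic, Hepatic failure, Acute hepatic failure and Hepatic necrosis, so a case coded to any of these is kept. SAP 7.9 also tabulates all treatment-emergent events, serious events and events leading to discontinuation, and it lists every event. SAP 7.10 with Appendix 2 summarises ALT and AST at 3, 5 and 10 times the upper limit of normal. None of these outputs depends on Appendix 3.

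**The case against.** The strongest reply is that the loss depends on things the documents do not settle.

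- **The selection column is not stated.** Matching on the first column would keep both terms. This stands, and it is why the consequence is conditional. It is also a reason to state the key.
- **Hepatitis B might not be counted.** If selection required class and PT together, and the dictionary files hepatitis B under infections, that row would match nothing. The documents do not show where MedDRA places it. This stands, so the wrong inclusion is only possible. Acute and fulminant hepatitis would still be missed under that rule.
- **The right PTs cannot be confirmed.** Nothing in the documents shows that acute or fulminant hepatitis is a current PT in the coding version. If it is not, no event can be coded to that term, and the question becomes which PT should replace it. This also stands, so the correction has to come from the dictionary.

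A reader might also infer a wider fault from the row for "Childhood disintegrative disorder", which shows a Child-Pugh score as its PT. The next row is the Child-Pugh row itself, and its PT cell is empty. That is what a one-cell shift in reading the table would produce, so it is not evidence of an error in the plan.

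Nor does the levetiracetam safety background add weight. Protocol 1.1 includes "hepatic failure, hepatitis, leukopenia, neutropenia" among post-marketing reports, but hepatic failure and hepatitis are both correctly present in the PT column.

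**Conclusion.** The two rows are wrong on their face and should be corrected. The severity is minor. The effect falls on one descriptive summary, and only if selection is on PT and an event is coded to one of the affected terms. The documents give no expected count of such events.

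A reader might go further and conclude that acute and fulminant hepatitis drop out of the safety reporting. They do not, because the outputs in step 5 of the working are independent of this list. A reader might also try to size the loss with confidence limits, for example by comparing 0 and 1 cases in 100 children. The SAP plans no interval for adverse events. The figure of 100 is the planned number of completers per group rather than the safety set, and enrolment stopped early (SAP section 1). Such limits would not describe any output of this study.

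**What to change.** 1. Check the two rows against the MedDRA version used to code the data, and correct the PTs so that acute and fulminant hepatitis are captured and Hepatitis B no longer stands in for acute hepatitis. Name that version: the appendix header cites 22.0 for class and 22.1 for PT, while SAP 7.9 allows 21.1 or higher.
2. Add one sentence to SAP 7.9 stating that events of interest are selected by matching the coded PT to the PT column of Appendix 3.
3. Check by program that each PT in Appendix 3 is the current one for its source term in that version.

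The cost is two appendix rows, one sentence and one programmed check. No data collection or other analysis changes. If the table has already been run, the full adverse event listing will show whether any child was affected.

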Oligohidrosis (decreased sweating) and hyperthermia, infrequently resulting in hospitalization, has been reported in clinical studies and post-marketing reports in association with the use of topiramate. These cases were characterized by decreased sweating and an elevation in body temperature above normal. Some of the cases were reported after exposure to elevated environmental temperatures. The majority of the reports have been in children. Skin erythema has been reported secondary to the hyperthermia and oligohidrosis and should be monitored; adequate hydration is encouraged.

Hyperammonemia and Encephalopathy

In clinical studies and post-marketing reports, concomitant administration of topiramate and valproic acid has been associated with hyperammonemia with or without encephalopathy in subjects who have tolerated either drug alone. In most cases, symptoms and signs abated with discontinuation of either drug. This adverse event is not due to a PK interaction.

Topiramate treatment has produced hyperammonemia (in some instances dose-related) in clinical studies in adolescents (12-16 years of age) who were treated with topiramate monotherapy for migraine prophylaxis and in very young pediatric subjects (1-24 months of age) who were

treated with adjunctive topiramate for POS. In some subjects, ammonia was markedly increased (defined in the clinical study report as >50% increase from baseline and absolute value >2x upper limit of normal [ULN]). In the adolescent subjects, the incidence of markedly increased hyperammonemia was 3% (1 subject), 0%, and 9% (3 subjects) for the placebo, 50 mg/day, and 100 mg/day groups, respectively.¹⁰

The hyperammonemia associated with topiramate treatment occurred with and without encephalopathy in placebo-controlled studies, and in an open-label extension study in infants. Dose-related hyperammonemia was also observed in the open-label extension study in pediatric subjects 1 month to 2 years of age. Clinical symptoms of hyperammonemic encephalopathy may include acute alterations in level of consciousness and/or cognitive function with lethargy or vomiting. Hyperammonemia with and without encephalopathy has also been observed in post-marketing reports in patients who were taking topiramate without concomitant valproic acid.³⁸

Kidney Stones

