1.2. Overall Rationale for the Study

Among its various pharmacologic actions, topiramate is a carbonic anhydrase inhibitor and may induce metabolic acidosis, and other changes (eg, hypocitraturia, hypercalciuria, and elevated urine pH) that may be associated with an increased tendency for kidney stone formation.⁴¹ Chronic metabolic acidosis may be associated with abnormal bone mineralization and/or homeostasis of vitamin D, calcium, or phosphorus. Childhood is a critical period for bone mineralization and growth. The effects of topiramate on growth, bone mineralization, and kidney stone formation have not been fully and systematically evaluated or well characterized in pediatric populations.

Preclinical juvenile rat studies demonstrated various clinical chemistry and bone findings (eg, changes in serum and urinary phosphate, decreased global BMD, decreased growth plate thickness) with topiramate treatment that raise concerns about long-term toxicities in pediatric patients.

This study will systematically assess the long-term safety of topiramate monotherapy compared with levetiracetam monotherapy; specific emphasis will be on metabolic acidosis related to topiramate therapy and its association with nephrolithiasis, BMD abnormalities, and delayed growth in children (2 to 15 years of age).

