Hydronephrosis repair	Surgical and medical procedures	Hydronephrosis repair
Hyperammonaemia	Metabolism and nutrition disorders	Hyperammonaemia
Hyperammonaemic encephalopathy	Nervous system disorders	Hyperammonaemic encephalopathy
Hyperbilirubinaemia	Hepatobiliary disorders	Hyperbilirubinaemia
Hypercalcaemia	Metabolism and nutrition disorders	Hypercalcaemia
Hypercalcaemic nephropathy	Renal and urinary disorders	Hypercalcaemic nephropathy
Hypercalciuria	Renal and urinary disorders	Hypercalciuria
Hypercholia	Hepatobiliary disorders	Hypercholia
Hypergammaglobulinaemia	Blood and lymphatic system disorders	Hypergammaglobulinaemia
Hyperglobulinaemia	Blood and lymphatic system disorders	Hyperglobulinaemia
Hyperhidrosis	Skin and subcutaneous tissue disorders	Hyperhidrosis
Hypermetropia	Eye disorders	Hypermetropia
Hyperplastic cholecystopathy	Hepatobiliary disorders	Hyperplastic cholecystopathy
Hyperpyrexia	General disorders and administration site conditions	Hyperpyrexia

Hypersomnia	Nervous system disorders	Hypersomnia
Hyperthermia	General disorders and administration site conditions	Hyperthermia
Hyperthermia malignant	General disorders and administration site conditions	Hyperthermia malignant
Hypertransaminaemia	Hepatobiliary disorders	Hypertransaminaemia
Hyperventilation	Respiratory, thoracic and mediastinal disorders	Hyperventilation
Hyphaema	Eye disorders	Hyphaema
Hypoalbuminaemia	Metabolism and nutrition disorders	Hypoalbuminaemia
Hypohidrosis	Skin and subcutaneous tissue disorders	Hypohidrosis
Hypophosphataemia	Metabolism and nutrition disorders	Hypophosphataemia
Hypophosphataemic rickets	Musculoskeletal and connective tissue disorders	Hypophosphataemic osteomalacia
Hypophosphatasia	Congenital, familial and genetic disorders	Hypophosphatasia
Hyposomnia	Psychiatric disorders	Hyposomnia
Hypothermia	General disorders and administration site conditions	Hypothermia
Icterus index increased	Investigations	Icterus index increased
Illogical thinking	Psychiatric disorders	Illogical thinking
Impaired self-care	General disorders and administration site conditions	Impaired self-care
Incoherent	Nervous system disorders	Incoherent
Initial insomnia	Psychiatric disorders	Initial insomnia
Intentional self-injury	Psychiatric disorders	Intentional self-injury
Intentional self-injury	Psychiatric disorders	Intentional self-injury
Iridoplegia	Eye disorders	Iridoplegia
Iritis	Eye disorders	Iritis
Ischaemic hepatitis	Hepatobiliary disorders	Ischaemic hepatitis

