Thought blocking	Psychiatric disorders	Thought blocking
Thought withdrawal	Psychiatric disorders	Thought withdrawal
Tongue exfoliation	Gastrointestinal disorders	Tongue exfoliation
Total bile acids increased	Investigations	Total bile acids increased
Toxic epidermal necrolysis	Skin and subcutaneous tissue disorders	Toxic epidermal necrolysis
Toxic skin eruption	Skin and subcutaneous tissue disorders	Toxic skin eruption
Transaminases abnormal	Investigations	Transaminases abnormal
Transaminases increased	Investigations	Transaminases increased
Tunnel vision	Nervous system disorders	Tunnel vision
Uhthoff's phenomenon	Nervous system disorders	Uhthoff's phenomenon

Ultrasound biliary tract abnormal	Investigations	Ultrasound biliary tract abnormal
Ultrasound bladder abnormal	Investigations	Ultrasound bladder abnormal
Ultrasound eye abnormal	Investigations	Ultrasound eye abnormal
Ultrasound kidney abnormal	Investigations	Ultrasound kidney abnormal
Ultrasound liver abnormal	Investigations	Ultrasound liver abnormal
Underweight	Metabolism and nutrition disorders	Underweight
Urea urine abnormal	Investigations	Urea urine abnormal
Urea urine decreased	Investigations	Urea urine decreased
Urea urine increased	Investigations	Urea urine increased
Urine abnormality	Renal and urinary disorders	Urine abnormality
Urine albumin/creatinine ratio abnormal	Investigations	Urine albumin/creatinine ratio abnormal
Urine albumin/creatinine ratio decreased	Investigations	Urine albumin/creatinine ratio decreased
Urine albumin/creatinine ratio increased	Investigations	Urine albumin/creatinine ratio increased
Urine bilirubin increased	Investigations	Urine bilirubin increased
Urine calcium decreased	Investigations	Urine calcium decreased
Urine calcium increased	Investigations	Urine calcium increased
Urine calcium/creatinine ratio decreased	Investigations	Urine calcium/creatinine ratio decreased
Urine calcium/creatinine ratio increased	Investigations	Urine calcium/creatinine ratio increased
Urine flow decreased	Renal and urinary disorders	Urine flow decreased
Urine homocystine present	Investigations	Urine homocystine present
Urine ketone body	Investigations	Urine ketone body
Urine ketone body present	Investigations	Urine ketone body present
Urine lactic acid decreased	Investigations	Urine lactic acid decreased
Urine lactic acid increased	Investigations	Urine lactic acid increased
Urine nitrogen	Investigations	Urine nitrogen
Urine odour abnormal	Renal and urinary disorders	Urine odour abnormal

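### Appendix 3, the only term list for adverse events of special interest, ties no term to a risk and includes terms opposite to the named risks, so any pooled count would include non-cases

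*SAP*

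**What the plan says.** SAP 7.9 commits to the analysis: "TEAEs by relationship and TEAEs of special interest will be summarized". The topiramate risks it names include "oligohidrosis, hyperthermia and secondary rash; hyperammonemia and/or encephalopathy; kidney stones", and it adds a shorter set for levetiracetam. It points to Appendix 3 "for the MedDRA codes for these AE of clinical interest", and neither document gives any other term definition.

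Appendix 3 has three columns: the reported term, the organ class (headed "AEBODSYS in MedDRA 22.0") and the preferred term. The rows are roughly alphabetical; one of them is "Urine calcium decreased". No column names a risk or a drug.

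The protocol gives a direction for two of these risks. On sweating and temperature, its Introduction says: "These cases were characterized by decreased sweating and an elevation in body temperature above normal". On stones, Section 1.2 lists "hypocitraturia, hypercalciuria, and elevated urine pH" among the changes linked to stone formation.

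The SAP 7.9 tables show incidence by arm, within age group and overall, ordered by organ class and then by preferred term, and an event listing is added. SAP Section 7 plans no formal tests.

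**The concern.** A special-interest summary is useful only if a counted child plausibly had the event in question. Read literally, one listed term is enough to make a child a special-interest case, even when the term is the reverse of the risk. Without a column assigning terms to risks, two programmers could build different counts for the same risk and both would be following the SAP.

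Sweating is the risk most exposed. No sweating assessment appears in the Time and Events Schedule, so adverse events carry that signal. With no test planned, the reported percentages are themselves the result.

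**Working it through.** **1. Listed terms against the protocol's direction.**

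| Risk as the protocol describes it | Listed terms in that direction | Listed terms in the opposite direction |
|---|---|---|
| Less sweating, raised temperature | Anhidrosis, Hypohidrosis, Hyperthermia, Heat stroke, Body temperature increased | Hyperhidrosis, Night sweats, Cold sweat, Hypothermia, Feeling cold, Body temperature decreased |
| Stones: high urine calcium, high urine pH | Urine calcium increased, Urine calcium/creatinine ratio increased, pH urine increased | Urine calcium decreased, Urine calcium/creatinine ratio decreased, pH urine decreased |

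Nitrite urine present and White blood cells urine positive are also listed. They are infection-type findings and are not part of the stone mechanism that the protocol gives.

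**2. What the planned table layout does with them.** Hyperhidrosis and Hypohidrosis share the skin organ class. Hypothermia and Hyperthermia share the general-disorders class. Raised and lowered urine calcium and pH share Investigations, with the urine infection findings. An organ-class or any-term count would pool each pair. Preferred-term rows cannot be added up into children per risk, because one child can have several terms. Terms for the sweating risk also cross classes: Heat stroke sits under injury and Hypohidrosis under skin.

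Several terms appear twice (Ammonia increased, Calculus bladder, Nephrolithiasis, Stag horn calculus, Temperature regulation disorder). That would fit separate risk lists having been merged and their labels lost, but the documents do not say so.

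**3. Size, as an illustration.** The documents give no precision for special-interest incidences. The nearest stated figure is for kidney stones in Protocol 11.2: 7% versus near zero, 100 completers per arm, Wilson score interval width 0.12. To reproduce it, the Wilson limits are 0.034 to 0.137 for 7/100 and 0 to 0.037 for 0/100. Combined by Newcombe's method:

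- lower limit = 0.070 - sqrt((0.070 - 0.034)² + 0.037²) = 0.019
- upper limit = 0.070 + (0.137 - 0.070) = 0.137
- width 0.119 from unrounded limits, which agrees with 0.12.

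Now let non-case terms affect a fraction b of each arm, equally and independently of true cases. Topiramate becomes 1 - (1 - b)(1 - 0.07), levetiracetam becomes b, and the difference becomes 0.07(1 - b). For b = 0.10: 1 - 0.90 × 0.93 = 0.163 versus 0.100, difference 0.063. Every b is an assumption.

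| b | Topiramate vs levetiracetam | Difference | 95% CI, 100 per arm | 95% CI, 141 per arm | Ratio |
|---|---|---|---|---|---|
| 0 | 7.0% vs 0% | 0.070 | 0.019 to 0.137 | 0.029 to 0.124 | – |
| 5% | 11.7% vs 5.0% | 0.067 | -0.012 to 0.149 | 0.001 to 0.135 | 2.33 |
| 10% | 16.3% vs 10.0% | 0.063 | -0.032 to 0.159 | -0.017 to 0.143 | 1.63 |
| 20% | 25.6% vs 20.0% | 0.056 | -0.061 to 0.171 | -0.042 to 0.153 | 1.28 |
| 30% | 34.9% vs 30.0% | 0.049 | -0.080 to 0.176 | -0.060 to 0.156 | 1.16 |

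The absolute difference moves little. The loss is in precision and in the ratio.

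For a rarer risk, assume 3% versus 0% with 100 per arm. The simple half-width is 1.96 × sqrt(0.03 × 0.97/100) = 3.3 points, so the interval already includes zero with clean terms. At b = 10% the rates are 12.7% versus 10% with half-width 8.8 points.

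**The case against.** A reader might infer that the list hides a topiramate signal. The documents do not support that.

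- SAP 7.9 reports every preferred term in its own row and adds a listing, so Hypohidrosis and Hyperhidrosis remain distinguishable.
- Neither document expressly specifies a pooled total per risk, and Protocol 11.4 says only that subjects with such events may be counted or listed.
- The primary concerns are measured directly: stones by ultrasound (SAP 7.1), weight and height (7.2, 7.3), bone density (7.4), bone markers (7.5) and laboratory and 24-hour urine values (7.10). Measured temperature has its own abnormal-value table (7.11).
- Unequal background rates could bias a pooled count in either direction.

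All of this stands, and it limits the point. It does not supply a count of children per risk, and it does not say which terms define each risk.

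Three further readings also go too far. Pyrexia might be called unrelated. It is non-specific, but raised temperature is part of the risk, so a broad search can reasonably keep it. Stone terms might be called scattered across organ classes. The core ones sit under renal and urinary disorders, with only marginal exceptions such as Calculus prostatic. Urine oxalate decreased and Urine uric acid decreased might be called reverse terms, but the protocol gives no direction for either.

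It can also be argued that a low urine calcium was meant for the growth and bone risk, since Protocol 1.2 links acidosis to calcium homeostasis. That is possible, but without an assignment column nobody can tell.

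**Conclusion.** The concern holds as a defect of definition. The sole term list for the special-interest summary does not map terms to risks, and it contains opposite-direction and infection-type terms. Any count above the preferred term would include non-cases and could be diluted.

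Dilution is possible but not shown. Its size rests on background rates the documents do not give, on those rates being equal between arms, and on an assumed arm size; SAP Section 1 reports that enrolment stopped early. A background of 10% or 20% would also be driven mostly by Pyrexia, so the table does not measure the gain from removing the opposite-direction terms alone.

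**What to change.** - Add a column to Appendix 3 assigning each term to a SAP 7.9 risk and to topiramate or levetiracetam.
- Remove the opposite-direction terms listed above, or state why each is kept. Do the same for Urine oxalate decreased and Urine uric acid decreased.
- Count each child once per risk and arm.
- For sweating and temperature, show a narrow count (for example Anhidrosis, Hypohidrosis, Hyperthermia, Heat stroke) beside a broad count that keeps Pyrexia.
- For stones, leave urinary infection findings out of the narrow count.

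The cost is an appendix edit and a few extra table rows, with no new data. A narrow count may miss a case coded only as Pyrexia, which the broad count still shows.
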